## 6.2. Adverse Events of Special Interest

Adverse events of special interest include skin rash, fall, fracture, and seizure, ischemic cerebrovascular disease and ischemic heart disease. A summary table by SOC and PT will be provided for AEs of special interest.

## 6.3. Adverse Events of Clinical Interest

Adverse events of clinical interest include cardiac disorders, diabetes, cognitive deficits. A summary table by SOC and PT will be provided for AEs of clinical interest.

## 6.4. Death

A summary of the number of deaths will be provided by time period (on-study vs during follow-up), along with the primary cause of death. Frequencies of on-study deaths due to study treatment-related adverse events will also be reported. A death is study intervention -related death if the primary cause is a drug related AE.

## 6.5. Clinical Laboratory Tests

All clinical laboratory tests will be displayed for the subjects included in the treated analysis set. A listing of participants with any laboratory results.

Laboratory data will be summarized by type of laboratory test. Descriptive statistics (mean, standard deviation, median and range) will be calculated for the raw data and for their changes from baseline at each time point of assessment. Toxicity grade will be summarized for hematology and chemistry parameters base on NCI-CTCAE. Change from baseline to the worst grade during the treatment will be provided as shift tables for selected parameters.

Liver function test data will be summarized based on eDISH and Hy's Law criteria ([FDA CDER CBER 2009](#)). Listings will be provided for subjects who meet the eDISH criteria and Hy's Law criteria, respectively.

## 6.6. Vital Signs and Physical Examination Findings

Descriptive statistics (mean, standard deviation, median and range) of pulse/heart rate, body temperature, and blood pressure (systolic and diastolic) values will be summarized at baseline. Changes from baseline will be summarized at each scheduled time point for blood pressure.

Vital signs and physical examination will be listed with abnormal observations indicated.

## 7. PHARMACOKINETICS/PHARMACODYNAMICS

### 7.1. Pharmacokinetics

PK analyses will be performed on the PK analysis set. The individual plasma apalutamide and the active metabolite N-desmethyl apalutamide concentrations will be listed. Apalutamide and N-desmethyl apalutamide plasma concentrations below the lowest quantifiable concentration or missing data will be labeled as such in the concentration data presentation.

Descriptive statistics (N, mean, SD, minimum, maximum, median, range, CV (%) ) will be used to summarize apalutamide and N-desmethyl apalutamide plasma concentrations at each sampling time point. Apalutamide and N-desmethyl apalutamide plasma concentrations below the lowest quantifiable concentration will be treated as zero in the summary statistics. If sufficient data are available, subgroup analysis by sex will be performed.

For concentration summary, applying the following rules.

- When more than half (>50%) of concentration data are below quantification limit (BQL) at each scheduled time point, mean and median will be reported as 'BQL'; SD and %CV are reported as 'NC'; maximum and minimum will be reported as observed (including BQL).
- When number of concentration data are equal to or less than 2, SD, %CV, median, minimum and maximum will be shown as 'NC' regardless of the proportion of BQL.

Data or subjects will be excluded from the analysis if the data do not allow for accurate assessment of the PK. All subjects and samples excluded from the analysis will be documented in the study report.

Additional analyses may be performed as deemed necessary. If sufficient data are available, then population PK analysis using plasma concentration data apalutamide and/or N-desmethyl apalutamide will be performed using nonlinear mixed-effects modeling. Details will be given in a population PK analysis plan and the results of the analysis will be presented in a separate report.

## 7.2. Pharmacokinetics/Pharmacodynamics

The relationship of exposure to apalutamide and N-desmethyl apalutamide to measures of efficacy and AEs may also be analyzed if sufficient data are available. Detailed plan and results for the analyses will be presented in separate documents.

## 8. BIOMARKER

Analyses are planned to explore exploratory biomarkers that may be indicative of the mechanisms of action of the drug or predictive of efficacy.

Biomarker analyses are dependent upon the availability of appropriate biomarker assays and clinical response rates. Biomarker analysis may be deferred or not performed, if during or at the end of the study, it becomes clear that the analysis will not have sufficient scientific value for biomarker evaluation, or if there are not enough samples or responders to allow for adequate biomarker evaluation.

Biomarker analyses will be performed on the treated analysis set.

The biomarkers that will support regulatory submission include tumor cell AR positivity (central) as well as the longitudinal enumeration and AR positivity of circulating tumor cells (CTCs) at baseline, Cycle 3 Day 1 and end-of-treatment (if available). The primary objectives of these analyses will be to explore the relationship between target expression on the tumor cells and response and the evaluation of CTC enumeration as a surrogate marker of response to therapeutic intervention.

Descriptive statistics for measured values and for changes from baseline at each scheduled time point for biomarkers will be provided. Frequency distribution with the number and percentage of subjects in each category will be provided. Treatment effect on ORR will be presented as odds

ratio (OR) estimated from logistic regression model comparing responders and non-responders and biomarker positive and biomarker negative populations. Box plots with distribution of biomarkers at each time point and response in ORR subgroups will be presented.

Further analysis of exploratory biomarkers may be performed, the detailed plans may be presented in a separate Translational Research Statistical Analysis Plan. Results of biomarker analyses may be presented in a separate report.

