4. STUDY DESIGN

4.1. Overall Design

This is an open-label, single-arm, multicenter, Phase 2 study to evaluate the efficacy and safety of apalutamide in combination with a GnRH agonist in participants with AR expressing locally advanced or recurrent/metastatic SGC.

A target of 24 participants will be included in this study and receive apalutamide and a GnRH agonist.

The study will consist of a screening phase, a treatment phase, and a follow-up phase. The study is anticipated to end approximately 42 months after the first participant is consented.

The study will be conducted in an outpatient setting and a treatment cycle is defined as 28 days. Study intervention will continue until disease progression, unacceptable toxicity, death, or the end of the study. Study intervention will be discontinued if a participant meets any of criteria described in Section 7.1, Discontinuation of Study Intervention.

After discontinuing study intervention, participants will be contacted every 6 months (refer to the SoA in Section 1.3) until death or the end of the study.

Participants will be monitored for safety starting from the signing of informed consent until 30 days after the last dose of study intervention. Adverse events including laboratory AEs will be graded and summarized using version 5.0 of the National Cancer Institute-Common Terminology Criteria for AEs (NCI-CTCAE). Dose modifications will be made as required according to dose modification rules (Section 6.6). An independent central radiology review will be used to reduce potential bias during data collection and evaluation of the primary endpoint of ORR and secondary endpoints including PFS (Section 9).

A diagram of the study design is provided in Section 1.2, Schema.

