6.3. Measures to Minimize Bias: Randomization and Blinding

Randomization will not be used in this study. All participants will receive the same study intervention.

As this is an open-label study, blinding procedures are not applicable.

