### **1.2. Trial Design**

This is an open-label, single-arm, multicenter, Phase 2 study to evaluate the efficacy and safety of apalutamide in combination with a GnRH agonist in participants with AR expressing locally advanced or recurrent/metastatic SGC.

The study will consist of a screening phase, a treatment phase, and a follow-up phase. Study intervention will continue until disease progression, unacceptable toxicity, death, or the end of the study. Study intervention will be discontinued if a participant meets any of criteria for discontinuation of study intervention. Dose modifications will be made as required according to dose modification rules. An independent central radiology review (ICRR) will be used to reduce potential bias during data collection and evaluation of the primary endpoint of overall response and secondary endpoints including progression-free survival (PFS).

An interim analysis will be performed when 12 response evaluable participants are observed for at least 24 weeks after the initiation of study intervention. Final analysis will be conducted when 24 response evaluable participants are observed for at least 24 weeks.

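### SAP Section 8 calls a marker–response odds ratio a treatment effect, and for central AR status that odds ratio may well have no finite estimate

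*SAP*

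**What the plan says.** SAP Section 8 reads "Treatment effect on ORR will be presented as odds" ratios, "estimated from logistic regression model comparing responders and non-responders and biomarker positive and biomarker negative populations". It names no exact, penalised or other sparse-data method and sets no minimum cell count. On the set used: "Biomarker analyses will be performed on the treated analysis set".

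The section gives these markers a role outside the trial: "The biomarkers that will support regulatory submission include tumor cell AR positivity (central"), together with CTC counts and AR positivity of CTCs over time. Its stated aims are to explore how target expression relates to response, and "the evaluation of CTC enumeration as a surrogate marker of response to therapeutic intervention".

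On design, SAP Section 1.2 says "This is an open-label, single-arm, multicenter, Phase 2 study", and Protocol Section 6.3 says "All participants will receive the same study intervention". Protocol Section 4.1 sets the size: "A target of 24 participants will be included in this study and receive apalutamide and a GnRH agonist". Protocol Section 5.1 (inclusion criterion 3) requires AR positivity by local test, at a cutoff of 1% of nuclei. Under Protocol Section 8.7 the central test checks that local result retrospectively.

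**The concern.** There are two separate problems.

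**The label.** Treatment does not vary in this trial, so no term in the model can estimate its effect. A higher response rate in marker-positives could mean that the marker identifies tumours the drug works on, or that such tumours do better on any therapy. One arm cannot separate these. A table headed as a treatment effect in material meant for a regulator invites the first reading.

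**Estimability for central AR status.** Entry selects on the local version of the marker that the model then splits. If the central-negative group is very small, it can easily contain no responders or only responders. The maximum-likelihood odds ratio is then zero or infinite and has no usable Wald interval. With no method stated in advance, a remedy would be chosen after the table has been seen.

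**Working it through.** **Plan's own figures.** The documents give no figure for the biomarker odds ratio. As a check on the design inputs, an exact two-stage binomial calculation was run with 12 then 24 participants, futility at 1 or fewer responders, and efficacy at 7 or more of 12 or 8 or more of 24. It gives type I error 1.33% at ORR 14% and power 80.5% at ORR 40%. These match the 1.3% and 80.5% in Protocol Section 9.5.

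**Inputs from the documents.** N = 24 treated (Protocol Section 4.1). ORR 40% and 14% are the design alternative and null (SAP Section 1.4).

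**Assumptions.** The number of central AR-negatives, m, is not given, so it is varied. ORR in marker-positives, pP, is set to 40%. ORR in marker-negatives, pN, is set to 40% (no association) or 14%.

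**Formula.** The maximum-likelihood odds ratio is finite only if all four cells of the marker-by-response table are non-zero. With k = 24 − m marker-positives,

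P(fail) = 1 − [1 − (1 − pN)^m − pN^m] × [1 − (1 − pP)^k − pP^k].

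For m = 0 the marker has one level. For m = 1 the first bracket is 1 − (1 − pN) − pN = 0. Failure is certain in both cases.

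For small m the second bracket is practically 1, so P(fail) ≈ (1 − pN)^m + pN^m:

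- m = 2, pN = 0.40: 0.36 + 0.16 = 0.52
- m = 2, pN = 0.14: 0.7396 + 0.0196 = 0.759
- m = 3, pN = 0.40: 0.216 + 0.064 = 0.28
- m = 3, pN = 0.14: 0.6361 + 0.0027 = 0.639

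Full formula:

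| Central negatives of 24 | P(fail), pN = 40% | P(fail), pN = 14% |
|---|---|---|
| 0 or 1 | 100% | 100% |
| 2 | 52% | 76% |
| 3 | 28% | 64% |
| 4 | 16% | 55% |
| 6 | 5% | 41% |
| 8 | 2% | 30% |
| 12 | 0.4% | 17% |

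If m is instead random with an assumed central-negative prevalence, the failure probability over the same two values of pN is 81% to 90% at 5% prevalence, 52% to 75% at 10%, and 18% to 51% at 20%.

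**What failure looks like.** Take 0/2 responders in negatives and 10/22 in positives. The ordinary fit returns a log odds ratio of about 20.4 with standard error about 12,500, which means the iterations stopped and nothing was estimated. For a 2×2 table Firth's penalty equals adding 0.5 to each cell, so OR = (10.5/12.5)/(0.5/2.5) = 4.2. The variance of the log OR is 1/10.5 + 1/12.5 + 1/0.5 + 1/2.5 = 2.575, so SE = 1.605. The Wald 95% interval is exp(1.435 ± 1.96 × 1.605), about 0.18 to 98: finite, but nearly uninformative.

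**The case against.** Much of the remedy is already planned. Protocol Section 3 lists ORR by AR-positivity as an exploratory endpoint, SAP Section 5.2.1 specifies Clopper-Pearson intervals for ORR, and SAP Section 2.3 extends subgroup analysis to all efficacy endpoints where numbers allow. An infinite odds ratio would not leave the marker question unreported. This stands.

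Section 8 lets biomarker analyses be dropped if they would lack scientific value, or if samples or responders are too few. The first ground could cover a table with two negatives, so the clause partly answers the point. It is discretionary, sets no cell count, and does not name few marker-negatives as a trigger.

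Firth and exact fits are also logistic regressions, so the SAP does not exclude them. That is true, but it does not name them either, and an unqualified logistic regression is normally run by maximum likelihood.

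Three stronger readings are tempting and not supported:

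- *The biomarker model fails in general.* Local AR entry does not directly restrict CTC counts, CTC AR positivity or genomic markers, and a more even split fails much less often.
- *The output will usually be inestimable.* The documents give neither the number of central negatives nor their ORR. Section 8 does not state the cutoff for its positive/negative split, and some subgroup rows in SAP Section 2.3 are redacted.
- *The SAP claims proven surrogacy or a proven predictive marker.* The section presents its aims as exploratory. The surrogate wording is loose, but no claim of validation is made.

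**Conclusion.** The label is wrong on the face of the text. This odds ratio is a marker–response association and cannot distinguish a predictive from a prognostic marker. The label also departs from the section's own aim of exploring a relationship, and from Protocol Section 9.4.5, which speaks of correlation with response.

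The estimability risk is real for central AR status, the first marker named, and its size depends on an unknown count. Under the stated assumptions the odds ratio cannot be estimated with 0 or 1 central negatives, and the failure probability is still 16% to 55% with 4.

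Severity is minor. Efficacy is declared solely on centrally reviewed ORR against fixed boundaries (SAP Sections 3 and 5.1.1). A reader might infer that the regulatory role given to these markers puts the trial's main conclusion at risk; nothing in the documents supports that.

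**What to change.** In SAP Section 8:

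1. Replace the treatment-effect label with *association between marker status and response*.
2. Lead with the already planned ORR by AR-positivity, with exact Clopper-Pearson intervals. Give the odds ratio second, from Firth-penalised or exact logistic regression. Report no odds ratio if one marker level is empty.
3. Describe the CTC objective as exploring association with response rather than surrogacy. A landmark analysis of Cycle 3 Day 1 CTC values against later outcome would be an optional addition.

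The cost is a few sentences in the SAP and a standard procedure, with no new data and no change to trial conduct. The drawback is that intervals will be very wide when negatives are few. No method can recover information that the sample does not contain.
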